7.3.1 Primary endpoint analyses

The primary and further pharmacokinetic endpoints (refer to Section 2.1.2 and 2.2.2.1) will be calculated according to the BI SOP ‘Standards and processes for analyses performed within Clinical Pharmacokinetics/ Pharmacodynamics’ (001-MCS-36-472). The non-compartmental analysis will be performed using a validated software program such as Phoenix WinNonlin™ software (version 6.3 or higher, Certara USA Inc., Princeton, NJ, USA) or SAS® Version 9.4 (or later version).

Primary analyses

The absolute bioavailability (F) will be estimated based on different administration methods of BI 1265162. As different doses are investigated among the administration methods, the primary endpoint (see Section 2.1.2) will be dose normalized for the statistical analysis. The statistical model used for the analysis of the primary endpoint will be an analysis of variance (ANOVA) model on the logarithmic scale. That is, the dose normalized PK endpoint will be log-transformed (natural logarithm) prior to fitting the ANOVA model. This model will include effects accounting for the following sources of variation: ‘sequence’, ‘subjects within sequences’, ‘period’ and ‘treatment’. The effect 'subjects within sequences' will be considered as random, whereas the other effects will be considered as fixed. The model is described by the following equation:

$$y_{ijkm} = \mu + \zeta_i + s_{im} + \pi_j + \tau_k + e_{ijkm}, \text{ where}$$

y_{ijkm} = logarithm of dose normalized $AUC_{0-\infty}$ measured on subject m in sequence i receiving treatment k in period j ,

μ = the overall mean,

ζ_i = the i^{th} sequence effect, $i = 1, 2, 3$

s_{im} = the effect associated with the m^{th} subject in the i^{th} sequence, $m = 1, 2, 3, 4$

π_j = the j^{th} period effect, $j = 1, 2, 3$

τ_k = the k^{th} treatment effect, $k = 1, 2, 3$

e_{ijkm} = the random error associated with the m^{th} subject in sequence i who received treatment k in period j .

where $s_{im} \sim N(0, \sigma_B^2)$ i.i.d., $e_{ijkm} \sim N(0, \sigma_W^2)$ i.i.d. and s_{im} , e_{ijkm} are independent random variables.

Point estimates for the ratios of the geometric means (T_i/R , $i=1, 2$), i.e. for the absolute bioavailability F , and their two-sided 90% confidence intervals (CIs) will be provided.

The difference between the expected means for $\log(T_i)-\log(R)$, $i=1, 2$, will be estimated by the difference in the corresponding adjusted means (Least Squares Means). Additionally their two-sided 90% confidence intervals will be calculated based on the residual error from the ANOVA and quantiles from the t-distribution. These quantities will then be back-transformed to the original scale to provide the point estimate and 90% CIs for each comparison of interest.

7.3.2 Secondary endpoint analyses

Not applicable.

7.3.4 Safety analyses

Safety will be analysed based on the assessments described in Section [2.2.2.2](#). All treated subjects (TS, refer to Section [7.3](#)) will be included in the safety analysis. Safety analyses will be descriptive in nature and based on BI standards. No hypothesis testing is planned.

For all analyses, the treatment actually administered (= treatment at onset) to the subject will be used (any deviations from the randomised treatment will be discussed in the minutes of the Report Planning Meeting).

Treatments will be compared in a descriptive way. Tabulations of frequencies/proportions will be used to evaluate categorical (qualitative) data, and tabulations of descriptive statistics will be used to analyse continuous (quantitative) data.

Measurements (such as ECG, vital signs, or laboratory parameters) or AEs will be assigned to treatments (see Section [4.1](#)) based on the actual treatment at the planned time of the measurement or on the recorded time of AE onset (concept of treatment emergent AEs). Therefore, measurements planned or AEs recorded prior to first intake of trial medication will be assigned to the screening period, those between first trial medication intake and end of REP (see Section [1.2.6](#)) will be assigned to the treatment period. Events occurring after the REP but prior to next intake or end of trial termination date will be assigned to 'follow-up'. These assignments including the corresponding time intervals will be defined in detail in the TSAP. Note that AEs occurring after the last per protocol contact but entered before final database lock will be reported to Pharmacovigilance only and will not be captured in the trial database.

Additionally, further treatment intervals (analysing treatments) may be defined in the TSAP in order to provide summary statistics for time intervals, such as combined treatments, on-treatment totals, or periods without treatment effects (such as screening and follow-up intervals).

Adverse events will be coded using the Medical Dictionary for Regulatory Activities (MedDRA). Frequency, severity, and causal relationship of AEs will be tabulated by treatment, system organ class, and preferred term. SAEs, AESIs (see Section [5.2.6.1](#)), and other significant AEs (according to ICH E3) will be listed separately.

Previous and concomitant therapies will be presented per treatment group without consideration of time intervals and treatment periods.

For safety assessments such as ECG, vital signs, or laboratory parameters, the baseline value is defined as the last measurement prior to drug administration on Day 1 of the respective treatment period.

Laboratory data will be compared to their reference ranges. A normalisation of lab values will not be performed as this is a single site with one local laboratory. Values outside the reference range as well as values defined as possibly clinically significant will be highlighted in the listings. Additionally, differences from baseline will be evaluated.

Vital signs or other safety-relevant data will be assessed with regard to possible on-treatment changes from baseline.

Relevant ECG findings will be reported as AEs.

7.4 EXPLORATORY PK ANALYSES

7.5 HANDLING OF MISSING DATA

7.5.1 Safety

It is not planned to impute missing values for safety parameters.

7.5.2 Pharmacokinetics

Handling of missing PK data will be performed according to the relevant Corporate Procedure ([001-MCS-36-472](#)).

PK parameters that cannot be reasonably calculated based on the available drug concentration-time data will not be imputed.

7.6 RANDOMISATION

Subjects will be randomised to one of the 3 treatment sequences (T1-T2-R-T3 or R-T1-T2-T3 or T2-R-T1-T3) in a 1:1:1 ratio. The block size will be documented in the CTR.

The sponsor will arrange for the randomisation as well as packaging and labelling of trial medication. The randomisation list will be generated using a validated system that uses a pseudo-random number generator and a supplied seed number so that the resulting allocation is both reproducible and non-predictable.

The randomisation list will contain additional blocks to allow for subject replacement (refer to Section [3.3.5](#)).

7.7 DETERMINATION OF SAMPLE SIZE

It is planned to enter a total of 12 subjects in the trial, because this sample size is considered sufficient to achieve the aims of this exploratory trial. With this sample size, the following precision in estimating the ratio of geometric means (T_i/R , $i=1, 2, 3$), i.e. the respective absolute bioavailability F , can be expected with 95% probability. Precision is defined as the

ratio of upper CI limit to the absolute BA estimate. Note that the precision is independent of the actual ratio of geometric means.

Table 7.7: 1 Precision that can be expected with 95% probability and illustrative two-sided 90% confidence intervals around the ratios of geometric means (T_i/R , $i=1,2,3$) for different gCVs in a 3x3 crossover trial (N=12)

gCV [%]	Precision upper CL / absolute BA estimate	Ratio [%]*	Lower CI limit [%]	Upper CI limit [%]
15.0	1.14	5	4.38	5.70
15.0	1.14	50	43.83	57.03
15.0	1.14	75	65.75	85.55
15.0	1.14	100	87.67	114.07
20.0	1.19	5	4.20	5.95
20.0	1.19	50	41.98	59.55
20.0	1.19	75	62.97	89.32
20.0	1.19	100	83.97	119.10
25.0	1.24	5	4.02	6.21
25.0	1.24	50	40.24	62.13
25.0	1.24	75	60.35	93.20
25.0	1.24	100	80.47	124.27

*Ratio of geometric means (T_i/R , $i=1,2,3$) for a PK endpoint is defined by $\exp(\mu_{T_i})/\exp(\mu_R)$.

The expected 90% confidence interval limits in the table were derived by

$$CI\ limit_{upper,lower} = \exp(\ln(\theta) \pm \omega),$$

with θ being the ratio (T_i/R , $i=1, 2, 3$) on original scale and ω the distance from the estimate θ to either confidence interval limit on the log-scale, which was obtained from the achievable precision on the original scale.

The calculation was performed as described by Julious [[R11-5230](#)] using R Version 3.5.1.

8. INFORMED CONSENT, TRIAL RECORDS, DATA PROTECTION, PUBLICATION POLICY, AND ADMINISTRATIVE STRUCTURE

The trial will be carried out in compliance with the protocol, the ethical principles laid down in the Declaration of Helsinki, in accordance with the ICH Harmonized Guideline for Good Clinical Practice (GCP), relevant BI Standard Operating Procedures (SOPs), the EU regulation 536/2014, and other relevant regulations. Investigators and site staff must adhere to these principles.

Standard medical care (prophylactic, diagnostic, and therapeutic procedures) remains the responsibility of the subject's treating physician.

The investigator will inform the sponsor immediately of any urgent safety measures taken to protect the trial subjects against any immediate hazard, as well as of any serious breaches of the protocol or of ICH GCP.

The Boehringer Ingelheim transparency and publication policy can be found on the following web page: trials.boehringer-ingelheim.com. As a general rule, no trial results should be published prior to archiving of the CTR.

The terms and conditions of the insurance coverage are made available to the investigator and the subjects, and are stored in the ISF.

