mode of admin.	Oral with 240 mL of water after an overnight fast of at least 8 h (T1)

Test product 2 dose mode of admin.	Drug formulation BI 1265162 solution for inhalation Inhaled by Respimat after an overnight fast of at least 8 h in combination with activated charcoal (T2) and without activated charcoal (T3).
Reference product dose mode of admin.	Drug formulation (R) BI 1265162 concentrate for infusion * Doses are tentative and may be adapted after first period (cf. 7.4) Intravenous over 1h after an overnight fast of at least 8 h
Duration of treatment	One day (single dose) for each treatment with a wash out period of at least 6 days between each treatment period
Statistical methods	Absolute bioavailability (F) will be estimated by the ratios of the geometric means (T_i/R , $i=1,2,3$) for the dose-normalized primary endpoint following oral and inhaled administrations. Additionally, their two-sided 90% confidence intervals (CIs) will be provided. This method corresponds to the two one-sided t-test procedure, each at a 5% significance level. Since the main focus is on estimation and not testing, a formal hypothesis test and associated acceptance range is not specified. The statistical model will be an analysis of variance (ANOVA) on the logarithmic scale including effects for sequence, subjects nested within sequences, period and treatment. CIs will be calculated based on the residual error from the ANOVA. Descriptive statistics will be calculated for all endpoints.

FLOW CHART – ORAL ADMINISTRATION (T1)

Period	Visit	Day	Planned time (relative to drug administration) [h:min]	Approximate clock time of actual day [h:min]	Event and comment	PK/Metabolites ^{blood}	Safety laboratory	12-lead ECG	Vital signs (BP, PR)	Questioning for AEs and concomitant therapy ⁶
SCR	1	-21 to -1			Screening (SCR) ¹		x	x	x	
1/2/3/4 (four periods separated by a wash-out of at least 6 days)	2/3/4	-1	-12:00	20:00	Admission to trial site (Device training if needed)		x ⁵			x
			1	-1:00	07:00	Allocation to treatment ² (visit 2 only) (Device training if needed)	x ²	x ²	x ²	x ²
	0:00	08:00		BI 1265162 administration + 240 mL fluid intake						
	0:30	08:30			x					
	0:45	08:45			x					
	1:00	09:00			x					
	2:00	10:00		240 mL fluid intake	x	x ⁷	x	x	x	
	3:00	11:00			x					
	4:00	12:00		240 mL fluid intake, thereafter lunch ³	x					
	6:00	14:00			x					
	8:00	16:00		Snack (voluntary) ³	x					
	11:00	19:00	Dinner							
	12:00	20:00		x				x		

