2	24:00	08:00	Breakfast (voluntary) ³ , discharge from trial site	x	x	x	x	x		
FU	6	3 to 7			End of trial (EOS) examination ⁴		x	x	x	x

1. Subject must be informed and written informed consent obtained prior to starting any screening procedures. Screening procedures include physical examination, check of vital signs, ECG, safety laboratory (including drug screening), demographics (including determination of body height and weight, smoking status and alcohol history), relevant medical history, concomitant therapy and review of inclusion/exclusion criteria. Pharmacogenetic samples will be collected if needed.
 2. The time is approximate; the procedure is to be performed and completed within the 3 h prior to drug administration.
 3. If several actions are indicated at the same time, the intake of meals will be the last action.
 4. At the end of trial visit the EoTrial examination includes physical examination, vital signs, ECG, safety laboratory, recording of AEs and concomitant therapies.
 5. Only urine drug screening and alcohol breath test will be done at this time
 6. AEs and concomitant therapies will be recorded throughout the trial, but will be specifically asked for at the times indicated in the Flow Chart above.
 7. Serum electrolytes only
- * At Visit 5/period 4 all subjects receive treatment T3

FLOW CHART – INTRAVENOUS ADMINISTRATION (R)

Period	Visit	Day	Planned time (relative to drug administration) [h:min]	Approximate clock time of actual day [h:min]	Event and comment	Intravenous admin.	PK/Metabolites ^{blood}	Safety laboratory	12-lead ECG	Vital signs (BP, PR)	Questioning for AEs and concomitant therapy ⁶	
SCR	1	-21 to -1			Screening (SCR) ¹			x	x	x		
1/2/3/4 (four periods separated by a wash-out of at least 6 days)	2/3 /4	-1	-12:00	20:00	Admission to trial site (Device training if needed)			x ⁵			x	
			1	-1:00	07:00	Allocation to treatment ² (visit 2 only) (Device training if needed)		x ²	x ²	x ²	x ²	x ²
				0:00	08:00	Start of BI 1265162 administration + 240 mL fluid intake	▲					
				0:05	08:05			x				
				0:30	08:30			x				
				0:59	08:59			x				
				1:00	09:00		▼			x	x	
				1:05	09:05			x				
				1:10	09:10			x				
				1:20	09:20			x				
				1:40	09:40			x				
				2:00	10:00	240 mL fluid intake		x	x ⁷	x	x	x ⁸
				2:30	10:30			x				
				3:00	11:00			x				
				3:30	11:30			x				
				4:00	12:00	240 mL fluid intake, thereafter lunch ³		x				
				5:00	13:00			x				
				7:00	15:00			x				
				8:00	16:00	Snack (voluntary)						

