4. CHANGES IN THE PLANNED ANALYSIS OF THE STUDY

Deviating from Section 7.3.4 in the CTP laboratory data will be analysed on normalised values.

If for some reason $AUC_{0-\infty}$ can not be calculated, AUC_{0-tz} will be used instead as the primary endpoint.

The PK analysis of absolute bioavailability will also be performed for the comparison T3/R. This will be done in the same way as the comparisons of T1 and T2 with R, which is described in Section 7.3.1 of the CTP.

All other analyses described in this TSAP are in accordance with the statistical methods described in the revised CTP.

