7.4 PRIMARY ENDPOINT

7.4.1 Primary analysis of the primary endpoint

Primary analysis of the primary endpoint will be performed as defined in Section 7.3.1 of the CTP.

To assess the absolute bioavailability of the treatments, the statistical model for the primary analysis defined in the CTP is an analysis of variance (ANOVA) model on the logarithmic scale including "sequence", "period" and "treatment" as fixed effects and "subject within sequence" as random effect. Absolute bioavailability of the study treatments will be estimated by the ratios of the geometric means of (T1/R), (T2/R) and (T3/R) of the primary endpoint.

Exclusion of plasma concentrations

The ADS ADPC (PK concentrations per time-point or per time-interval) contains column variables ACEXC or ACEXCO indicating inclusion/exclusion (ACEXC) of a concentration and an analysis flag comment (ACEXCO). Exclusion of a concentration depends on the analysis flag comment ACEXCO. For example, if ACEXCO is set to "ALL CALC", the value will be excluded for all types of analyses based on concentrations. If ACEXCO is set to "DESC STATS" the value will be excluded from descriptive evaluations per planned time point/time interval. If ACEXCO contains the addition "TIME VIOLATION" or "TIME DEVIATION", the value can be used for further analyses based on actual times. If ACEXCO is set to "HALF LIFE", the value will be excluded from half-life calculation only; the value is included for all other analyses. Excluded concentration itself will be listed in the CTR associated with an appropriate flag.

Exclusion of PK parameters

The ADS ADPP contains column variables APEXC and APEXCO indicating inclusion/exclusion (APEXC) of a PK parameter and an analysis flag comment (APEXCO). All analyses based on the PKs are based on PK parameter values which are not flagged for exclusion, i.e. with APEXC equal to "Included".

Further details are given in "Noncompartmental Pharmacokinetic / Pharmacodynamic Analyses of Clinical Studies" (4) and "Description of Analytical Transfer Files and PK/PD Data Files" (5).

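### SAP 4 and 7.4.1 extend the period-adjusted ANOVA to T3/R, which it cannot estimate because T3 is aliased with period 4; Table 7.7: 1 also labels its crossover precision as covering T3/R

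*Protocol*

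**What the plan says.** The three sequences in Protocol 7.6 are T1-T2-R-T3, R-T1-T2-T3 and T2-R-T1-T3. The inhaled flow chart adds: "At Visit 5/period 4 all subjects receive treatment T3". R therefore occurs only in periods 1 to 3.

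Protocol 7.3.1 writes a model with three sequences, three periods and three treatments. It promises "Point estimates for the ratios of the geometric means (T_i/R , $i=1, 2") only, and each log difference "will be estimated by the difference in the corresponding adjusted means (Least Squares Means"). The synopsis, however, lists T_i/R for i=1,2,3 and describes one ANOVA "including effects for sequence, subjects nested within sequences, period and treatment. CIs will be calculated based on the residual error from the ANOVA".

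SAP 4 adds T3/R as a change to the planned analysis, to be done "in the same way as the comparisons of T1 and T2 with R, which is described in Section 7.3.1 of the CTP". SAP 7.4.1 describes the model as "including 'sequence', 'period' and 'treatment' as fixed effects", with subject within sequence random, and lists T1/R, T2/R and T3/R together.

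Protocol 7.7 opens its precision statement with "With this sample size, the following precision in estimating the ratio of geometric means" and indexes it i=1,2,3. The table title ("for different gCVs in a 3x3 crossover trial (N=12")), the footnote and the formula legend use the same index.

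**The concern.** T3/R is the absolute bioavailability after inhalation without charcoal, one of the three ratios under the main objective. A model with a period factor separates treatment from period only where treatments share periods. T3 shares its period with nothing. An analyst who fits the model that SAP 4 and 7.4.1 point to, on data that include period 4, gets no T3/R estimate. Some restriction on period 4 then has to be chosen, and several are available. They give different interval widths and rest on an assumption that this design cannot check.

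The label in 7.7 adds to the problem. A reader would take T3/R to be protected against period effects in the same way as T1/R and T2/R. Any period-4 shift would instead pass in full into T3/R.

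**Working it through.** **Inputs.** N = 12, four per sequence (Protocol 7.6, 7.7 and the model in 7.3.1). Two-sided 90% CI, half-width met with 95% probability, gCV 15, 20 and 25% (Table 7.7: 1). Sequences as in 7.6.

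**1. Reproduce the table.** With σ = √ln(1+gCV²), the log half-width is

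ω = t(0.95, df) · σ · √v · √(χ²(0.95, df)/df), and precision = exp(ω).

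For R, T1 and T2 in periods 1 to 3 there are 36 observations and the design matrix has rank 16. So df = 20 and v = 2/12 = 1/6. The constants are t = 1.7247, χ² = 31.410 and √(31.410/20) = 1.2532. At gCV 25%, σ = 0.24622 and

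ω = 1.7247 × 0.24622 × 0.40825 × 1.2532 = 0.2173, so precision = 1.2427.

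At 15% and 20% the results are 1.1407 and 1.1910. At a ratio of 50% and gCV 25% the limits are 40.24 and 62.13, as printed. All 12 rows match. The table is the precision of the randomised 3x3 part.

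**2. Is T3/R estimable when period is a full factor?** A contrast is estimable only if adding it as a row leaves the rank of the design matrix unchanged.

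| Data fitted | n | Rank | Residual df | T3/R |
|---|---|---|---|---|
| R, T1, T2, T3 | 48 | 17 | 31 | not estimable |
| R, T2, T3 | 36 | 16 | 20 | not estimable |
| R, T3 | 24 | 15 | 9 | not estimable |

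The T3 column and the period-4 column are identical. Treating subject as random does not help: the fixed part has rank 8, and 9 once the contrast is added. T1/R and T2/R remain estimable.

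**3. T3/R once a period-4 assumption is made.** In each case v = 1/6.

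| Model for T3/R | df | gCV 15% | gCV 20% | gCV 25% |
|---|---|---|---|---|
| Paired T3 − R, no period term | 11 | 1.1575 | 1.2143 | 1.2731 |
| R, T2, T3; period 4 = mean of periods 1–3 | 20 | 1.1407 | 1.1910 | 1.2427 |
| Four treatments; period 4 = mean of periods 1–3 | 31 | 1.1324 | 1.1796 | 1.2279 |

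For the paired line at gCV 25%, t = 1.7959 and √(19.675/11) = 1.3374. Then ω = 1.7959 × 0.24622 × 0.40825 × 1.3374 = 0.2414, so precision = 1.2731. At a ratio of 50% the paired interval is 39.28 to 63.65, against 40.24 to 62.13 in the table.

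With complete data the paired and four-treatment models give the same point estimate and differ only in width.

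**4. What a period-4 shift would do.** R is spread equally over periods 1 to 3. The mean of T3 − R therefore estimates the true log ratio plus the period-4 effect minus the average effect of periods 1 to 3. Illustration only, with assumed shifts that are not in the documents: a true F of 50% becomes 0.50 × 1.05 = 52.5% with a +5% shift, or 0.50 × 1.10 = 55% with +10%.

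**The case against.** **The table is nearly right for T3/R anyway.** This stands. Against the table, the paired analysis differs by 0.017, 0.023 and 0.030, and one constrained model reproduces the table exactly. The table's own step from gCV 15% to 25% is 0.10. Protocol 7.7 sets no precision target and calls the trial exploratory, and 7.2 specifies no formal test. A reader might infer that the sample size is miscalculated or N too small; nothing in the documents supports that.

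**The model in 7.3.1 has only three period levels, so the aliasing arises only if a fourth is added.** True as written, but the model also has only three treatment levels and yields ratios for T1 and T2. It has no term for a fourth period or a fourth treatment. Bringing T3 in means either adding period 4, which aliases it, or restricting period 4, which is the assumption that goes unstated. A reader might also infer that the adjusted means for T1/R and T2/R fail. They do not under 7.3.1, and those two differences remain estimable even with four period levels.

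**Unseen text may hold a T3/R model.** Protocol 7.3.3 and the body of 7.4 are not in the available text, SAP section numbers are skipped, and SAP 6.1 refers to an ADS Plan for technical detail. So one cannot say that no T3/R model exists anywhere. But SAP 4 points only to 7.3.1, and SAP 7.4.1 does the same.

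**The fixed last treatment is openly disclosed.** It is, in the title and the design sections. Disclosing the order does not state the analysis assumption that the order makes necessary.

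**Conclusion.** The concern holds in a limited form. As written, SAP 4 and 7.4.1 tie T3/R to a period-adjusted model that cannot estimate it, and the available text gives no period-4 assumption that would make it estimable. Table 7.7: 1 is correct for T1/R and T2/R, and its i=3 label attributes that precision to a comparison that is not a period-adjusted crossover comparison. The effect on stated precision is small, about 0.02 to 0.03 for the paired analysis. T1/R, T2/R and N are unaffected.

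A reader might go further and infer that T3/R is biased. The documents do not show that: they give no evidence of a period-4 effect, and the shifts above are assumed. What can be said is that such an effect would enter T3/R in full and could not be detected in this design.

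The precision figures assume complete data on 12 subjects and a common within-subject variance. The estimability result needs only the three sequences and a full period factor.

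**What to change.** 1. In SAP 4 and 7.4.1, or in the CTR if the SAP is closed, name an estimable T3/R model without a period-4 term. The simplest is the within-subject paired analysis of log dose-normalised AUC0-∞, T3 minus R, with a t-based 90% CI on 11 df. State that it assumes no period-4 effect, that this design cannot test the assumption, and that any such effect passes in full into T3/R. Keep T1/R and T2/R on the 7.3.1 model and make the synopsis agree.
2. Limit the lead-in, title, footnote and legend of Protocol 7.7 to i=1,2. Add a T3/R line from the named model; for the paired analysis it is 1.16/1.21/1.27 at gCV 15/20/25%.
3. If text not available here already states a T3/R model, cross-reference it instead.

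A pooled four-treatment fit on 31 df is possible but not the better default. It adds an equal-variance assumption across routes and gives the non-randomised ratio a narrower planned interval (1.23 at gCV 25%) than the randomised ones (1.24). In a simulation with assumed log-scale SDs of 0.35 for T3 and 0.10 for the other treatments, its 90% CI covered about 79%, against about 90% for the paired analysis.

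The cost is a few sentences, an index change and one added line, with a slightly wider stated precision for T3/R. N, conduct and data collection do not change.
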